8.2 Safety

Baseline is the last safety assessment prior to the date of randomization.

Adverse Events and Concomitant Medications:

Adverse events with missing severity will be assigned the highest severity. Adverse events with missing relationship will be assigned as related, as part of a sensitivity analysis. Adverse events and Concomitant Medications with partial dates will be imputed according to the algorithm defined in the SDTM specifications.

Treatment Compliance:

Treatment compliance will be determined for the entire double blind treatment period. The total tablets taken = total tablets dispensed - total tablets returned. Compliance = 100 x Total tablets taken / Total tablets Expect

Eisai Final 4.0 Confidential Page 22 of 30

Echocardiogram:

The aortic and mitral valve regurgitation will be categorized as absent, trace, mild, moderate or severe. FDA-defined valvulopathy, or simply "FDA valvulopathy," stipulate that significant valvular regurgitation comprises mild or greater aortic valve regurgitation and/or moderate or greater mitral valve regurgitation. The ECHO data presents the mitral and aortic valve severity as 5 categories; ABSENT, TRACE, MILD, MODERATE, and SEVERE.

For each subject and visit a dichotomous variable will be created, where;

1 = mild or greater aortic valve regurgitation and/or moderate or greater mitral valve Regurgitation

0 = aortic valve regurgitation is absent or trace and mitral valve regurgitation is mild or less.

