9.4.3 Method of Assigning Subjects to Treatment Groups

Subjects will be assigned to treatments based on a computer-generated randomization scheme that will be reviewed and approved by an independent statistician. The randomization scheme and identification for each subject will be included in the final clinical study report for this study.

After the Baseline Period, subjects will be randomized to 1 of 2 treatment groups in a ratio of 1:1. Each treatment group will receive either lorcaserin or placebo BID.

Randomization will be performed centrally by an interactive voice and web response system (IxRS). The IxRS or clinical supply vendor will generate the randomized bottle identification numbers. At enrollment (and after successful completion of Visit 1), the investigator or designee will call the IxRS to register the subject information. At randomization (Visit 2), the IxRS will assign each subject a unique 6-digit randomization number. At every subsequent dose change, the investigator or a designee will call the IxRS to obtain dispensing instructions and register the subject's visit.

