9.5.1.1 Screening Assessments

9.5.1.1.1 DEMOGRAPHY

Subject demography information will be collected at the Screening Visit. Demography information includes date of birth, sex, race/ethnicity.

Height and weight will be measured at the Screening Visit.

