9.5.1.4.10 OTHER SAFETY ASSESSMENTS

C-SSRS

An assessment of suicidality using the C-SSRS will be performed at Screening, Baseline, Day 1 postdosing, every visit, including after the last dose of study drug, and at the Termination Visit, as designated in the Schedule of Procedures/Assessments ([Table 3](#)).

Pregnancy Test

A serum β -hCG test will be performed for female subjects age 12 years old and above, or of child-bearing potential, only. A sample of blood will be taken at Screening; at all other time points a urine pregnancy test will be performed as specified in the Schedule of Procedures/Assessments ([Table 3](#)). If urine cannot be obtained for pregnancy testing after Screening, a serum pregnancy test will be performed.

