9.5.2 Schedule of Procedures/Assessments

9.5.2.1 Schedule of Procedures/Assessments

[Table 3](#) presents the Schedule of Procedures/Assessments for the Core Study.

Table 3 Schedule of Procedures/Assessments in Study E2023-A001-304: Core Study

Phase	Prerandomization	Randomization									
Period	Screening/Baseline	Treatment ^a							Follow-up ^{b,c}		
Visit	1	2	3	4	5	6	7	8		ED ^d	Unscheduled ^e
Week	From -4 Weeks to Week 0	0	1	2	4	6	10	14	4 weeks after the last dose		
Procedures/Assessments											
Demography	X										
Informed consent/assent	X										
Inclusion/exclusion criteria	X	X									
Medical history	X										
Epilepsy history ^f	X										
Prior and concomitant medications	X	X	X	X	X	X	X	X	X	X	X
Prior and concomitant AEDs	X	X	X	X	X	X	X	X	X	X	X
Adverse events	X	X	X	X	X	X	X	X	X	X	X
Randomization		X									
Study drug compliance			X	X	X	X	X	X		X	X ^{e,g}
Dispense study drug		X	X	X	X	X	X	X ^h			X ^{e,g}
Retrieve unused study drug			X	X	X	X	X	X		X	X ^{e,g}
Dispense subject's diary	X	X	X	X	X	X	X	X ^h			X ^e
Retrieve and review diary		X	X	X	X	X	X	X		X	X ^e
Neurological examination ⁱ	X							X		X	

Table 3 Schedule of Procedures/Assessments in Study E2023-A001-304: Core Study

Phase	Prerandomization	Randomization									
Period	Screening/Baseline	Treatment ^a							Follow-up ^{b,c}		
Visit	1	2	3	4	5	6	7	8		ED ^d	Unscheduled ^e
Week	From -4 Weeks to Week 0	0	1	2	4	6	10	14	4 weeks after the last dose		
Procedures/Assessments											
Physical examination ⁱ	X							X		X	
Vital signs, and weight	X	X	X	X	X	X	X	X		X	X ^e
Height	X										
Clinical laboratory tests ^j	X					X		X		X	X ^{e,k}
Serum β-hCG test ^l	X										
Urine pregnancy test ^l		X						X		X	X ^e
12-Lead ECG ^m	X							X		X	X ^{e,k}
Echocardiogram	X							X		X	X ^{e,k}
PK sampling (plasma) ⁿ			X	X	X	X				X ^o	
IxRS call	X	X	X	X	X	X	X	X		X	X ^e
C-SSRS	X	X	X	X	X	X	X	X		X	
QoL		X						X		X	
Clinical Global Impression ^p		X						X		X	

AE = adverse event, AED = antiepileptic drug, β-hCG = beta-human chorionic gonadotropin, COVID-19 = Coronavirus disease 2019,

C-SSRS = Columbia-Suicide Severity Rating Scale, ECG = electrocardiogram, ED = early discontinuation, IxRS = interactive voice and web response system,

Table 3 Schedule of Procedures/Assessments in Study E2023-A001-304: Core Study

Phase	Prerandomization	Randomization									
Period	Screening/Baseline	Treatment ^a							Follow-up ^{b,c}		
Visit	1	2	3	4	5	6	7	8		ED ^d	Unscheduled ^e

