Week	From -4 Weeks to Week 0	0	1	2	4	6	10	14	4 weeks after the last dose		
Procedures/Assessments											

PedsQL = Pediatric Quality of Life Inventory, PK = pharmacokinetic, QoL = Quality of Life in Epilepsy Scale/Pediatric Quality of Life Inventory 4.0; QOLIE-31 = Quality of Life in Epilepsy Survey.

- a: All visits to be done within ± 3 days of the schedule. If any of the visits after Visit 1 are conducted remotely due to the COVID-19 pandemic, at a minimum, the following assessments should be conducted: AEs, suicidality assessment, concomitant medications, review of seizure diary data, and study drug compliance (any missed or extra doses with dates). Study drug and seizure diary may be picked up from the site by the subject/caregiver or shipped from the site to the subject's location. C-SSRS and Clinical Global Impression may be conducted remotely over the phone by a qualified rater and QOLIE-31 and PedsQL based on input from subject over the phone.
- b: Visit to be done within ± 7 days of the schedule.
- c: The Follow-up Visit only applies to those subjects who do not enter the Extension Phase after completion of this study.
- d: These assessments will be conducted for subjects who discontinue the study or treatment early for any reason after Visit 2.
- e: At Unscheduled Visits these assessments/procedures conducted if needed.
- f: Epilepsy history will include information on genetic mutation related to epilepsy, if available.
- g: Unused study drug to be retrieved and study drug dispensed only for subjects requiring dose change at Unscheduled Visits.
- h: Study drug and seizure diary will be dispensed only for subjects who enter the Extension Phase.
- i: Physical and neurological examinations will only be performed at the indicated visits. For all other clinic visits during the study, the physical and the neurological examinations will only be performed when there is a complaint from the subject. Clinically significant abnormal findings from the physical or the neurological examinations will be reported as AEs.
- j: Clinical laboratory tests include hematology, blood chemistry, and urinalysis.
- k: At Unscheduled Visits, these assessments will only be done if the results from the previous visit were deemed clinically significant by the investigator.
- l: Only for female subjects of child-bearing potential (defined as all postmenarche females, unless postmenopausal or have been sterilized surgically).

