8.3 Definition of Visit Windows

Table 3 of the protocol presents the schedule of procedures/Assessments. The screening/baseline period is four weeks long and procedures/assessments are performed at randomization, weeks 1, 2, 4, 6, 10, and 14 of the treatment period with a follow-up of 4 weeks after end of treatment. Table 3 presents the protocol specified visits/weeks and corresponding time windows used for visit-wise analyses are presented in terms of days relative to the randomization. If more than one measurement is included in a visit window, the measurement collected closest to the scheduled date will be used in the analysis. In the case where two measurements were collected an equal number of days before and after the Scheduled Day the later of the two measurements will be used for analysis. For ECHO assessments when assessing a new or worsened event then the most severe assessment will be selected if 2 or more assessments fall within a visit window

Eisai Final 4.0 Confidential Page 23 of 30

Table 3 Visit Windows Measurements

Scheduled	Scheduled Week	Scheduled	Time Window (Days)	
1	Screening		First day of Screening	-1
2	Baseline/ Randomization	1	1	
3	1	7	2	10
4	2	14	11	17
5	4	28	18	34
6	6	42	35	48
7	10	70	49	82
8	14	98	83	101
Extension Phase				
9	15	105	102	110
10	17	119	111	125
11	20	140	126	149
12	23	161	150	169
13	26	182	170	194

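### SAP 8.2 ends the safety baseline before the randomization date, so the Visit 2 vital signs and weight cannot be baseline, although SAP Table 3 labels that visit as baseline

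*SAP*

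**What the plan says.** - **Baseline rule.** SAP 8.2: "Baseline is the last safety assessment prior to the date of randomization". The cut-off is a calendar date, with no exception for a reading taken on that date before dosing. No other section gives a different safety baseline.
- **Visit label.** SAP 8.3 counts days from randomization. In its Table 3 the screening window closes at Day −1, and Visit 2 is Day 1 with the label "Baseline/ Randomization". The same section says "The screening/baseline period is four weeks long".
- **When randomization happens.** Protocol 9.4.3: "At randomization (Visit 2), the IxRS will assign each subject a unique 6-digit randomization number".
- **What is measured.** Protocol Table 3 marks the row "Vital signs, and weight" at Visit 1, at Visit 2 and at each later treatment visit. Height is marked at Visit 1 only, in line with Protocol 9.5.1.1.1: "Height and weight will be measured at the Screening Visit".
- **Where the baseline is used.** SAP 5.6 summarizes weight and BMI changes. SAP 5.6.4 presents vital signs and weight, with their changes from baseline, for each visit and arm.
- **What survives termination.** SAP Section 7, written with 22 subjects randomized, keeps descriptive statistics for the secondary endpoints. SAP 5.1.3 lists safety among them.

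**The concern.** The visit that the SAP calls baseline is the one visit that its baseline rule shuts out. For vital signs and weight, the protocol collects a reading on the randomization date, and SAP 8.2 passes over it for one taken nominally four weeks earlier. Each on-treatment change then mixes treated time with untreated run-in.

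Weight is a pertinent safety measure here. Protocol 7.1 records that the drug was approved for weight management. The case series in Protocol 7.2 reports decreased appetite, weight loss and a fall in BMI. Enrolment starts at age 2. With inferential analyses dropped, the descriptive safety tables are a main part of what the trial will report, so their reference point should be unambiguous.

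**Working it through.** The plan states no figure to reproduce. The check applies the rule to the visit schedule and then counts days.

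**Step 1: which reading qualifies.** Visit 2 is the randomization date, which is Day 1. The rule requires a date before Day 1, so Visit 2 fails. The only earlier scheduled reading is Visit 1. An unscheduled reading between the two visits would replace Visit 1 for that subject.

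**Step 2: which measures move.**

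| Measure | Scheduled at Visit 1 | Scheduled at Visit 2 | Baseline depends on the rule? |
|---|---|---|---|
| Vital signs, weight | yes | yes | yes |
| BMI | yes | weight only | through weight only |
| C-SSRS | yes | yes | only if the Visit 2 assessment is predose |
| Laboratory tests, ECG, echocardiogram | yes | no | no |

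On the C-SSRS, Protocol 9.5.1.4.10 says that it "will be performed at Screening, Baseline, Day 1 postdosing, every visit", while Protocol Table 3 has a single mark at Visit 2. The documents do not say which Day 1 assessment that mark stands for.

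**Step 3: interval length at scheduled days.** Inputs are Day 1 for Visit 2, Day 7 for Week 1 and Day 98 for Week 14 (SAP Table 3), with an assumed run-in of 28 days, the planned length.

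- Week 14 from Visit 2: 98 − 1 = 97 days. From Visit 1: 97 + 28 = 125 days. Run-in share: 28 / 125 = 22%.
- Week 1 from Visit 2: 7 − 1 = 6 days. From Visit 1: 6 + 28 = 34 days. Run-in share: 28 / 34 = 82%.

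**Step 4: range.** Footnote a of Protocol Table 3 says "All visits to be done within ± 3 days of the schedule". Applied to Visit 2, the run-in is 25 to 31 days. Applied to Visit 8 as well, Week 14 falls on Days 95 to 101.

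- From Visit 2: 95 − 1 = 94 to 101 − 1 = 100 days.
- From Visit 1: 94 + 25 = 119 to 100 + 31 = 131 days.

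Whatever the date of the later visit, the excess equals the run-in: 25 to 31 days under these windows, and less if the run-in is shorter. These are lengths of time, not estimates of change in weight or vital signs.

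**The case against.** The strongest reply is that nothing is broken. SAP 8.2 is the only safety baseline rule and it is clear. Table 3 of the SAP assigns measurements to visit windows, and its label derives nothing. Protocol Table 3 places Visit 1 under screening and baseline and Visit 2 under the randomization phase. SAP 8.1 also ends the efficacy baseline on the day before randomization. A cut-off that is certain to precede treatment is a legitimate convention. Moreover, no section says that the Visit 2 readings are taken before dosing. The list in Protocol 11.5 of items recorded directly on the CRF includes sampling times for drug concentrations and laboratory tests but not times for vital signs. If timing cannot be confirmed, a revised rule might return many subjects to Visit 1. Finally, SAP Section 9 leaves programming derivations to separate documents, which may already deal with Day 1.

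Part of this stands. Excluding Day 1 may be deliberate, and the gain from a change depends on the Visit 2 readings being predose. But the SAP gives no such reason. The efficacy convention suits diary counts, where Day 1 has to go to one period or the other; it is a weaker argument for a single reading that may precede the dose. Elsewhere the SAP anchors to treatment: prior medication (5.2.5) and exposure (5.6.1) to the first dose, and treatment-emergent events (5.6.2) to the pretreatment state. Quality of life, which 8.2 does not govern, is collected before treatment only at Visit 2, yet SAP 5.7 summarizes its change from baseline. So the plan does rely on Visit 2 as a baseline elsewhere. If the programming documents already handle Day 1, the SAP text should say the same.

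**Conclusion.** The point holds as a minor one. Taken literally, SAP 8.2 contradicts the label in SAP Table 3 and moves the baseline for vital signs, weight and the weight part of BMI to Visit 1. At scheduled days this lengthens the Week 14 change from 97 to about 125 days. That figure assumes a 28-day run-in and no unscheduled reading between the two visits.

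A reader might infer more than the documents support:

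- **That the Visit 2 reading is lost.** It is not. It has its own window and would appear as a row in the by-visit tables of SAP 5.6.4, so drift over the run-in can be seen. It is nonetheless carried into every later change from baseline.
- **That the comparison between arms is biased.** The same rule and run-in apply to both arms, so no systematic shift is expected in the Core Study. Efficacy analyses do not use this baseline.
- **That the valvulopathy, laboratory or ECG summaries are affected.** None of these assessments is scheduled at Visit 2, so their baselines are the same under either rule.
- **That weight change is misstated by some amount.** The documents give no basis for estimating one.
- **That the suicidality summary in SAP 5.6.6 must change.** The timing of the Visit 2 C-SSRS is not settled, so this is only a question for the sponsor.

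**What to change.** 1. In SAP 8.2, define the safety baseline for vital signs, weight and BMI as the last non-missing assessment before the first dose of study drug. Say that predose readings on the randomization date count.
2. State one convention for Day 1 readings whose timing relative to first dose cannot be confirmed, for example using the Visit 1 value, and footnote how many subjects it affects.
3. Make the Visit 2 label in SAP Table 3 agree with the rule, and check that the programming specifications match.
4. For the C-SSRS, ask the sponsor to confirm whether the Visit 2 assessment is predose or postdose. No change to SAP 5.6.6 is shown to be needed.

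The cost is one or two sentences of SAP text and a change to a derivation, with no new assessments. The downside is small: someone must confirm when the Visit 2 readings were taken relative to the first dose, and if few can be confirmed, the tables will change little.

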7.2 Clinical Experience

Tolete et. al (2018) summarize a retrospective chart review (Jan 2014 – Jan 2018) of 36 patients with childhood-onset refractory epilepsies (Dravet syndrome [20 patients], Lennox-Gastaut syndrome [9 patients], other treatment-resistant focal epilepsies [3 patients], and generalized epilepsies [3 patients]) administered lorcaserin. Thirty-three (94.3%) patients were taking at least 1 antiseizure medication (mean = 3; clobazam [60%], valproic acid [57.1%], and cannabidiol [40%]). Of the 35 patients analyzed, the median percentage reduction from baseline in the mean monthly frequency of motor seizures was 47.7% ($z=-3.04$, $P<0.01$; 46.9% in tonic-clonic, 62.3% in tonic, 60.1% in atonic, and 54.6% in focal seizures with motor features); 15 (42%) had greater than 50% reduction in motor seizures. Two (5.7%) patients had increased seizure frequency. The mean lorcaserin dosage was 15.7 mg/d (and 13.7 mg/d for children) and median treatment duration was 10.8 months. After 15 months, 50% of patients remained on lorcaserin. The most common AEs reported were decreased appetite (19.6%), decreased attentiveness (17.1%), and weight loss (11.1%). The mean decline in body mass index (BMI) at last follow-up compared to baseline was $-0.58 \pm 0.24 \text{ kg/m}^2$ ($-2.7 \pm 1.3\%$; $P=0.02$) and was similar among patients taking or not taking valproate. Five patients stopped treatment before 30 days due to side effects. The above nonclinical and clinical information on lorcaserin justifies the development of lorcaserin in Dravet.

The study design and duration of treatment was selected based on Guidelines for Industry on Clinical Evaluation of Antiepileptic Drugs (FDA, 1997) and is similar to the design of registration clinical studies of Epidiolex, drug approved for treatment of Dravet syndrome (Devinsky et al., 2017) and recently reported fenfluramine study in Dravet syndrome (Lagae et al., 2020). Sample size was estimated based on the percent reduction of convulsive seizures and standard deviation reported in fenfluramine study in Dravet syndrome (Lagae et al., 2020).

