Appendix 2 Extension Phase

Study Design and Plan

The Extension Phase will consist of a Treatment Period (12 weeks) and a Follow-up Period (4 weeks). Subjects are eligible to complete the Extension Phase only if they have completed the Treatment Period of the Core Study.

All subjects will receive lorcaserin during entire Extension Phase but the dose level will be blinded during the first 6 weeks. During the first 6 weeks of the Extension Phase, subjects who received lorcaserin during the Core Study will receive the same dose of lorcaserin (the dose will remain flexible per weight category, based on clinical response and tolerability); subjects who received placebo during the Core Study will receive the target dose of lorcaserin per weight category. During the second 6 weeks of the Extension Phase, all subjects will receive lorcaserin at the maximum dose per weight category (the dose may be decreased due to tolerability reasons and increased again if tolerability improves). Addition, deletion, and dose changes to concomitant antiepileptic drugs (AEDs) are not allowed during the Treatment Period of the Extension Phase.

The Follow-up Visit will be conducted 4 weeks after the last dose of study drug for subjects who will not participate in the Extended Access Program (Study E2023-A001-405) after completion of this study.

The objectives of the Extension Phase are:

- To evaluate the safety and tolerability of lorcaserin
- To characterize the pharmacokinetics (PK) of lorcaserin and the relationship between lorcaserin plasma concentrations, efficacy, and safety
- To summarize the efficacy of lorcaserin as measured by percent change in frequency of convulsive seizures
- To summarize the efficacy of lorcaserin as measured by percent change in frequency of each type of seizure
- To summarize the efficacy of lorcaserin as measured by proportion of subjects who are free from convulsive seizures
- To summarize the efficacy of lorcaserin as measured by proportion of subjects who are seizure-free
- To summarize the efficacy of lorcaserin as measured by percent change in frequency of clusters
- To summarize the efficacy of lorcaserin as measured by Clinical Global Impression of Change
- To summarize the efficacy of lorcaserin as measured by on quality of life

Schedule of Procedures/Assessments

Table 4 presents the Schedule of Procedures/Assessments for the Extension Phase.

Table 4 Schedule of Procedures/Assessments in Study E2023-A001-304: Extension Phase

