Statistical analyses will be performed by the sponsor or designee after the study is completed, the database is locked and released, and a snapshot of the database is obtained and released. Analyses for regional submissions may be performed during the course of the study. Statistical analyses will be performed using SAS software or other validated statistical software, as required. Details of the statistical analyses will be included in a separate statistical analysis plan.

Statistical and Analytical Plans

The statistical analyses of Extension Phase data are described in this section. Further details of the analytical plan will be provided in the statistical analysis plan, which will be finalized before database lock and treatment unblinding.

Study Endpoints

- Safety and tolerability, including incidence of treatment-emergent adverse events
- PK parameters of lorcaserin in the Treatment Period
- Percent change in frequency of convulsive seizures
- Percent change in frequency of each type of seizure
- Proportion of subjects who are free from convulsive seizures
- Proportion of subjects who are seizure-free
- Percent change from baseline in frequency of clusters
- Clinical Global Impression of Change
- Change from baseline in QOLIE-31 and PedsQL 4.0 Scales

Analysis sets

Safety Analysis Set is the group of subjects who received at least 1 dose of study drug and had at least 1 postdose safety assessment in the Extension Phase.

Full Analysis Set is the group of subjects who received at least 1 dose of study drug and had at least 1 postdose seizure measurement in the Extension Phase.

Efficacy Analyses

Descriptive statistics will be provided for the efficacy endpoints in the Extension Phase. Mean, standard deviation, median, minimum, and maximum will be provided for continuous endpoints and number and percentage will provide for categorical variables. In addition, plots will be used to summarize the data.

Safety Analyses

All safety analyses will be performed on the Safety Analysis Set. Safety data that will be evaluated include monitoring and recording all adverse events; regular laboratory evaluation for hematology, blood chemistry, and urinalysis; periodic measurement of vital signs, weight and ECGs; and the performance of physical and neurological examinations. Safety analyses will be performed similarly to the Core Study analyses and all analyses will be on the treatment duration (Core Study and Extension Phase).

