3.2 Overall Study Design and Plan

This is a multicenter, multiple-dose, randomized, double-blind, placebo-controlled, parallel-group adjunctive therapy study in subjects with Dravet syndrome. The study is planned to be conducted in US, Canada, India, and China or Brazil (to be determined). The study will consist of a Core Study and open-label Extension Phase.

The Core Study will include a Prerandomization and a Randomization Phase.

The Prerandomization Phase will include a Screening/Baseline Period (4 weeks), during which the subjects will be assessed for eligibility.

Once the Screening and Baseline procedures have been completed and eligibility has been established, the subjects will be randomized and begin treatment in the Randomization Phase. Approximately 62 subjects will be randomized to 1 of 2 treatment groups in a ratio of 1:1 and will receive lorcaserin or placebo for 14 weeks. The randomization will be centralized and stratified by previous treatment with fenfluramine (yes, no) and by weight categories (10 to <20 kg, 20 to <40 kg, and ≥40 kg). The stratification factors will be balanced between treatment groups using restricted randomization method proposed by Pocock and Simon (1975).

The Randomization Phase will consist of 2 periods: Treatment Period (14 weeks) and Follow-up Period (4 weeks).

During the Treatment Period, all subjects will take study drug twice daily (BID) based on weight category at randomization, as described in Section 9.4.1 of the protocol.

For lower weight categories, during the first 2 weeks of Treatment Period, the dose may be increased (not earlier than after 1 week of treatment) by 1 dose level at a visit. If the dose was increased, in the event of AEs, according to the investigator's clinical judgment, the dose may remain the same or can be decreased by 1 dose level, to the Target dose at any time during the Treatment Period. If the dose had been decreased, it may be increased again if tolerability improves.

All subjects who complete the Core Study will be eligible to enter the Extension Phase (refer to Appendix 2 of the protocol). The last visit of the Treatment Period of the Core Study is considered to be the 1st visit of the Extension Phase.

The Follow-up Visit will be conducted 4 weeks after the last dose of study drug for subjects who do not enter the Extension Phase.

Eisai Final 4.0 Confidential Page 9 of 30

dose

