5.9 Extension Phase Analyses

Efficacy Analyses

Descriptive statistics will be provided for the efficacy endpoints in the Extension Phase. Mean, standard deviation, median, minimum, and maximum will be provided for continuous endpoints and number and percentage will provide for categorical variables. In addition, plots will be used to summarize the data. Efficacy analyses will be performed similarly to the Core Study analyses and all analyses will be on the treatment duration (Core Study and Extension Phase).

Safety Analyses

All safety analyses will be performed on the Safety Analysis Set. Safety data that will be evaluated include monitoring and recording all adverse events; regular laboratory evaluation for hematology, blood chemistry, and urinalysis; periodic measurement of vital signs, weight and ECGs; and the performance of physical and neurological examinations. Safety analyses will be performed similarly to the Core Study analyses and all analyses will be on the treatment duration (Core Study and Extension Phase).

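### Extension safety changes in former placebo subjects are measured from a pre-randomization baseline, 14 to 18 weeks before their first lorcaserin dose

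*SAP*

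**What the plan says.** SAP 8.2 states the safety baseline once, with no exception for the Extension: "Baseline is the last safety assessment prior to the date of randomization".

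For the Extension, SAP 5.9 says "Safety analyses will be performed similarly to the Core Study analyses" and sets the period as the Core Study and Extension combined. Protocol Appendix 2 gives the same instruction. The visit windows in SAP 8.3 also count Extension visits from randomization.

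Protocol Appendix 2 says that "subjects who received placebo during the Core Study will receive the target dose of lorcaserin per weight category". SAP 3.2 fixes when this happens: "The last visit of the Treatment Period of the Core Study is considered to be the 1st visit of the Extension Phase". First lorcaserin in these subjects therefore follows Visit 8.

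SAP 5.6.3 summarizes laboratory change from baseline, compares baseline with later low/normal/high class in shift tables, and defines a TEMAV (except for phosphate) as a rise from baseline to grade 2 or higher. SAP 5.6, 5.6.4 and 5.6.5 plan change summaries for weight, BMI, vital signs and ECG.

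Other rules were adapted to the Extension. Appendix 2 redefines the analysis sets, and SAP 5.2.5 and 5.6.2 adjust the concomitant-medication and treatment-emergent windows. The baseline was not adapted.

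**The concern.** The first objective listed for the Extension is the safety and tolerability of lorcaserin. A former placebo subject has a clean pre-lorcaserin measurement at Visit 8, where protocol Table 3 schedules weight, vital signs, laboratory tests and ECG. The written rule passes over it and goes back to before randomization. The Extension change in that subject then mixes placebo time with lorcaserin time and measures the effect of neither.

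Two kinds of output are exposed. Subject-level classifications (shift tables and TEMAVs) can attribute to the lorcaserin period something that was already present at the end of placebo. Continuous summaries carry whatever drift occurred on placebo. For weight in growing children that drift is upward. It runs against the weight loss (11.1%) and mean BMI fall (2.7%) that protocol 7.2 cites from a chart review of lorcaserin.

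SAP 7 makes this more relevant. After termination it cuts the efficacy, subgroup, sensitivity and PK analyses but does not withdraw safety, so safety is a main remaining output.

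**Working it through.** **Inputs**
- Core treatment: SAP 3.2, subjects "will receive lorcaserin or placebo for 14 weeks".
- Visit days: SAP 8.3, Table 3. Screening ends on Day -1, randomization is Day 1 (no Day 0), Visit 8 is Day 98 and Visit 13 is Day 182.
- Earliest baseline: protocol 9.1.1.1 has screening run from Week -4, so baseline falls between Day -28 and Day -1.
- Pretreatment schedule: in protocol Table 3, laboratory tests and ECG appear only at Visit 1. Weight and vital signs are also taken at Visit 2, but that is the randomization date, which the wording of 8.2 excludes.
- Subjects: SAP 7, 22 randomized. SAP 3.2, about 62 planned, 1:1.

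**The plan's own figures.** Core: 98/7 = 14.0 weeks. Extension: (182 - 98)/7 = 12.0 weeks. Fraction randomized: 22/62 = 35%. All agree with the documents.

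**Time before lorcaserin.** With no Day 0, the days from Day -b to Day d are d + b - 1.

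| Baseline on | To first lorcaserin (Day 98) | To Visit 13 (Day 182) | Share before lorcaserin |
|---|---|---|---|
| Day -1 | 98 + 1 - 1 = 98 days = 14.0 weeks | 182 + 1 - 1 = 182 days = 26.0 weeks | 98/182 = 54% |
| Day -28 | 98 + 28 - 1 = 125 days = 17.9 weeks | 182 + 28 - 1 = 209 days = 29.9 weeks | 125/209 = 60% |
| Visit 8 (proposed) | 0 | 182 - 98 = 84 days = 12.0 weeks | 0% |

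The 3-day visit window moves the gap by at most 3/7 = 0.4 week. SAP Table 3 labels Visit 2 as baseline, in conflict with 8.2. Under that label the gap for weight and vital signs would be 98 - 1 = 97 days (13.9 weeks), so the conflict does not change the conclusion.

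**Subjects affected.** 22/2 = 11 at most, approximately, and fewer after Core dropouts. In a group of 11, one misattributed TEMAV moves the rate by 1/11 = 9 percentage points.

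**The TEMAV rule applied to two hypothetical placebo subjects**

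| Visit 1 | Visit 8, end of placebo | Visit 13, on lorcaserin | TEMAV at Visit 13, current rule | TEMAV at Visit 13, Visit 8 baseline |
|---|---|---|---|---|
| Normal | Grade 2 | Grade 2 | Yes | No |
| Grade 2 | Normal | Grade 2 | No | Yes |

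The current rule can both add and drop events. Shift tables behave the same way. In addition, a highest or lowest value taken over the combined period may itself come from the placebo weeks.

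**Weight, illustration only.** ASSUMPTION, not in the documents: growth of 1 to 4 kg per year. Growth before lorcaserin is rate x weeks/52:
- over 14 weeks, 1 x 14/52 = 0.27 kg to 4 x 14/52 = 1.08 kg;
- over 18 weeks, 1 x 18/52 = 0.35 kg to 4 x 18/52 = 1.38 kg.

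In a 20 kg child this is 0.27/20 = 1.3% to 1.38/20 = 6.9%.

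Now ASSUME growth of 2 kg per year and a lorcaserin effect of -0.5 kg:
- current baseline: 2 x 26/52 - 0.5 = +0.50 kg to 2 x 30/52 - 0.5 = +0.65 kg;
- Visit 8 baseline: 2 x 12/52 - 0.5 = -0.04 kg.

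The reset removes the pre-switch growth, but not the growth during the Extension itself.

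**The case against.** **Planned by-visit tables already show the switch.** Weight, vital signs and laboratory values are summarized by visit, so a reader could compare Visit 8 with later visits. This has force for group means. It depends on Extension tables being split by Core arm, which the SAP does not state, and on the same subjects being present at both visits. It cannot repair shift or TEMAV counts, which are fixed subject by subject against the earlier baseline.

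**Another document may define an Extension baseline.** SAP 9 and 11 place the derivation rules and table shells in separate documents, which were not available here. That is possible, but the only rule in the SAP says otherwise and should be corrected there.

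**The affected group is small and the phase is uncontrolled.** Both are true. With about 11 subjects, individual values can be read in listings, and the controlled safety comparison is the Core Study, where one pre-randomization baseline suits both arms. This limits the importance of the point. It does not make the Extension tables correct.

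**A Visit 8 baseline still leaves growth in the result.** This stands. Up to 12 weeks of growth remain mixed with any drug effect.

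**Conclusion.** The point holds. Followed as written, the SAP gives former placebo subjects an Extension change from baseline of which 54% to 60% of the span to Visit 13 precedes lorcaserin. It also keeps placebo-onset laboratory abnormalities in the Extension shift and TEMAV counts. The timing rests on nominal visit days. The figure of about 11 subjects rests on 1:1 allocation of the 22 randomized; the documents do not say how many entered the Extension.

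A reader might infer more than the documents support:
- *That a weight loss of known size would be hidden or turned into a gain.* No growth rate is given. The 2.7% in protocol 7.2 is a BMI fall at last follow-up in a chart review with median treatment of 10.8 months, and cannot be carried over to weight in a 12-week Extension. Inclusion has no upper age limit and there is a stratum of 40 kg or more, so not every subject is growing. Masking is plausible, but its amount is unknown.
- *That drift on placebo would mimic lorcaserin weight loss.* Growth acts in the opposite direction. False attribution to lorcaserin is shown here only for persisting laboratory abnormalities.
- *That all Extension safety data are affected.* Protocol Table 4 schedules no echocardiogram, so scheduled Extension echocardiograms are not affected. For subjects on lorcaserin throughout, the pre-randomization baseline is appropriate.

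**What to change.** In SAP 5.9 and 8.2, for Extension safety summaries:
- In former placebo subjects, define baseline as the last assessment before the first lorcaserin dose, normally Visit 8, and count only values after that dose.
- Apply this to weight, vital signs, laboratory change, shift and TEMAV tables, and ECG.
- Keep the pre-randomization baseline for subjects on lorcaserin throughout, and present the two groups separately.
- In the same edit, reconcile 8.2 with the baseline label on Visit 2 in SAP Table 3.

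**Cost.** SAP wording, a second baseline flag in the analysis datasets and extra tables. Weight, vital signs, laboratory tests and ECG are already scheduled at Visit 8, so no new data are needed. Height is the exception: it is scheduled only at Visit 1, so a Visit 8 BMI would rest on screening height and should be footnoted. Growth over the 12 uncontrolled Extension weeks remains and should be stated as a limitation.
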